2. Summary of study procedures – cont-d

Period	Visit	Day	Planned time (relative to drug administration) [h:min]	Approximate clock time of actual day [h:min] ²⁶	Event and comment ¹⁶	Spirometry ^{3,25}	Medical examination	12-lead ECG	Vital signs (BP, PR)	Safety lab ^{19,20,21,22}
			24:45	08:45						
			25:00	09:00	Bolus MCh challenge⁹	X ¹⁸		X	X	
			25:30	09:30						
			26:00	10:00	250mL water intake, thereafter breakfast					
			27:00	11:00						
			28:00	12:00	250mL water intake, thereafter lunch					
			32:00	16:00	snack (voluntary)					
			33:00	17:00	Discharge from trial site			X	X	X ²¹
End of Treatment	6	+14 ^{6,27,15}			End of trial (EOT) examination ¹⁵	X	X	X	X	X

Guidance Notes

1	All subjects must sign an informed consent consistent with ICH-GCP guidelines prior to participation in the trial, which includes medication washout and restrictions.
2	Screening within 14 days before drug administration including review of inclusion and exclusion criteria, relevant medical history, demographics, concomitant medication, physical examination and review of vital signs/ECG/laboratory, Flexibility in scheduling and repeating screening or baseline procedures according to investigator judgement is permitted. Patient's consent can be obtained prior to the screening period.
3	
Spirometry is performed at the screening visit (Visit 1) and Treatment period 1 – Day 1 to determine eligibility for participation in the study.
 
Treatment Periods 2 to 4 – Day 1, eligibility to dose based on the predose FEV % of predicted will be assessed by clinical judgment of the investigator.
 
Prior to methacholine challenge the subject's FEV₁ should be within the range (\geq 70% of predicted normal*) on Day -2 to Day -1 and at Day 2 at Visits 2-5 (Treatment Periods 1 to 4)
 
*Clinical judgement may be applied in borderline cases.

4	
5	Timepoint included for technical (database set-up) reasons only
6	AEs and changes in concomitant therapies will be monitored and recorded throughout the trial
7	Incremental MCh challenge during Visit 1 will use an escalation protocol to determine the PD20 in a given volunteer.
8	In exceptional circumstances, the washout between the two treatment periods can be extended up to a maximum of 8 weeks

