3. DESCRIPTION OF DESIGN AND TRIAL POPULATION

3.1 OVERALL TRIAL DESIGN AND PLAN

This multiple dose, randomised, placebo controlled, trial will be conducted in two parts. The first part (pilot study) will be a single-blind four-way crossover with dose ordered sequences. The second part (main study) will be a double-blind four-way crossover, conducted according to a William's design. In both parts of the study, BI 443651 or placebo equivalent will be administered three consecutive times, 12 hours apart, per dose level. All subjects will receive placebo, 100, 400 and 1200 µg BI 443651 (in Part 1, the dose groups may be altered in case evolving data suggests a change in dosage is required (see below)). Each period will be separated by a washout period of at least 14 days (and not more than 28 days). Two administrations of BI 443651 will be delivered on Day 1 (morning and evening) and a single administration Day 2 (morning). One hour after dosing on Day 2, MCh challenge will be performed. A methacholine challenge will be conducted on Day -2 to Day -1 for each treatment period, (with the Day -2 to Day -1 challenge providing the baseline for each treatment period) at the same time of the day.

The two parts of the study will be conducted as follows:

Part 1: 4 subjects will be included in the first pilot part of the study each being administered three active doses of BI 443651 and placebo, with the active doses investigated being in ascending order of dose strength. Placebo administered given in a single-blinded manner in any order relative to the active treatment as per Table 3.1:1.

Table 3.1:1 Sequences for pilot part of the study

Treatment Period 1	Treatment Period 2	Treatment Period 3	Treatment Period 4
Placebo	100 µg	400 µg	1200 µg
100 µg	Placebo	400 µg	1200 µg
100 µg	400 µg	Placebo	1200 µg
100 µg	400 µg	1200 µg	Placebo

Part 2: 32 subjects will participate in the trial with each subject being administered three active dose levels of BI 443651 and placebo. This part of the study will be fully randomised, double blind. The decision to proceed to Part 2 will be based upon the safety and tolerability data of Part 1. Part 2 will only be conducted if, in the opinion of the investigator, no safety concerns arose in Part 1 and if none of the pre-specified trial-specific stopping criteria were met ([see Section 3.3.4.2](#)).

Table 3.1:2

Sequences for main part of the study

Treatment Period 1	Treatment Period 2	Treatment Period 3	Treatment Period 4

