3.2 DISCUSSION OF TRIAL DESIGN, INCLUDING THE CHOICE OF CONTROL GROUP(S)

For MCh challenge studies, the crossover design described in [Section 3.1](#) is commonly employed to increase sensitivity due to the within subject comparison. An active comparator is not appropriate for this assessment and a placebo comparison is required as a negative control to quantify the nature of any response observed.

Subjects will be allowed to continue inhaled low dose corticosteroid and SABA use provided washout is undertaken prior to MCh challenge. The subjects will be on standard of care treatment for the severity of their disease and thus the use of placebo in this setting is considered acceptable.

The study will be conducted in two parts: Part 1 in 4 subjects in a dose escalating design and Part 2 in which doses may be administered according to a William's crossover design (i.e. highest may be administered first). Three multiple dose levels of BI 443651 are included, to assess for a dose-effect relationship as observed in the nonclinical studies and also, in part one of the study to allow for effects to be assessed at lower doses prior to subjects being exposed to the highest dose as the initial dose (as may be allowed in Part 2 of the study). For the pilot part (Part 1), it is planned to include 4 asthma subjects. The planned sample size is not based on a power calculation. This sample size is considered sufficient for the initial evaluation of safety post MCh challenge prior to allowing patients to be administered the highest dose of BI 443651 as the first dose level.

For the main part (Part 2), it is planned to include a total of 32 (8 per sequence) subjects with mild asthma, because this sample size is considered sufficient to achieve the aims of this exploratory trial. For more details refer to [Section 7.7](#).

The cumulative bolus dose approach to MCh challenge is used during the treatment phases as the primary outcome is based on drop in FEV1 for a given dose rather than dose of MCh required to achieve a fall in FEV1.

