7. STATISTICAL METHODS AND DETERMINATION OF SAMPLE SIZE

7.1 STATISTICAL DESIGN – MODEL

The primary objective of the study is to investigate safety and tolerability of three consecutive administrations, 12 h apart, at three different dose-levels (100, 400 and 1200 µg) of BI 443651 administered via oral inhalation in male and female mild asthmatic subjects after a bolus MCh challenge.

For the main part, the primary endpoint absolute change in maximum reduction of FEV₁ and the secondary endpoint relative change in AUC_{0-tz} as described in [Section 5.1](#) will be analysed using a mixed effects model on the original and logarithmic-scale, respectively, taking the crossover design of the trial into account. The models will include treatment and period as fixed effects, subject as a random effect and period baseline as well as subject baseline as covariates. The subject baseline will be obtained by calculating the mean of period baselines for each subject. Active doses will be compared to placebo for both endpoints. For investigation of the secondary endpoint time to recovery to within 95% of post-diluent value a Cox proportional hazards model will be used to estimate the hazard ratio of BI 443651 vs. Placebo.

For the pilot part, the primary and secondary endpoints as described in [Section 5.1](#) will be analysed using descriptive statistics. No inferential statistics are planned for this part of the trial.

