7.6 RANDOMISATION

For each trial part, subjects will be randomised to one of four treatment sequences (see [Section 3.1](#)) in a 1:1:1:1 ratio. The block size will be documented in the CTR.

The sponsor will arrange for the randomisation as well as packaging and labelling of trial medication. The randomisation list will be generated using a validated system, which involves a pseudo-random number generator and a supplied seed number so that the resulting allocation is both reproducible and non-predictable.

The randomisation list will contain additional blocks to allow for subject replacement (refer to [Section 3.3.5](#)).

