6. GENERAL ANALYSIS DEFINITIONS

6.1 TREATMENT(S)

For basic study information on treatments to be administered please refer to Section 4 of the CTP.

The trial is composed of two parts: The first part (pilot study) will be a single-blind four-way crossover with dose ordered sequences. The second part (main study) will be a double-blind four-way crossover, conducted according to a William's design. In both parts of the study, BI 443651 or placebo equivalent will be administered three consecutive times, 12 hours apart, per dose level. All subjects will receive placebo, 100, 400 and 1200 µg BI 443651. Each period will be separated by a washout period of at least 14 days (and not more than 28 days). Two administrations of BI 443651 will be delivered on Day 1 (morning and evening) and a single administration on Day 2 (morning).

Table 6.1: 1 Treatments and labels used in the analysis (for both trial parts)

Treatment		Short label
P	Placebo, respimat, bid	Plc
A	BI 443651 Respimat, 1*100 mcg/actuation, ih, bid	BI 100
B	BI 443651 Respimat, 4*100 mcg/actuation, ih, bid	BI 400
C	BI 443651 Respimat, 4*300 mcg/actuation, ih, bid	BI 1200

Table 6.1: 2 Overview of treatments for intra-individual comparison

Test treatment (T)		Reference treatment (R)	
BI 100	(A)	Placebo	(P)
BI 400	(B)	Placebo	(P)
BI 1200	(C)	Placebo	(P)

Measurements (such as ECG, vital signs, or laboratory parameters) or adverse events (AE) will be assigned to treatments and study periods by applying the following rules:

- **Screening:** measurements planned or AEs recorded prior to first device actuation for administration of trial medication.
- **On-treatment:** measurements planned or AEs recorded between first device actuation for administration in one treatment period until first device actuation for administration of trial medication in the next treatment period or until the end of the respective residual effect period (REP) or until trial completion date (whichever occurs first) will be assigned to the preceding treatment. The REP for BI 443651 is defined as after the last trial medication application.

- **Follow-up:** measurements planned or AEs recorded between the end of REP of one treatment period and the first device actuation for treatment administration of the next treatment period or trial completion date. In case of more treatments, the follow-up will be summarized according to the previous treatment.

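### Part 2 is called a William's design, but the sequences in Table 3.1:2 are a Latin square without first-order carryover balance

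*Protocol*

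**What the plan says.** Protocol Section 3.1 describes Part 2 thus: "The second part (main study) will be a double-blind four-way crossover, conducted according to a William's design". Section 3.2 says that "doses may be administered according to a William's crossover design", and SAP Section 6.1 again has a "double-blind four-way crossover, conducted according to a William's design".

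Table 3.1:2, titled "Sequences for main part of the study", is the only list of Part 2 sequences in either document:

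| Sequence | Period 1 | Period 2 | Period 3 | Period 4 |
|---|---|---|---|---|
| 1 | P | 100 | 400 | 1200 |
| 2 | 100 | P | 1200 | 400 |
| 3 | 400 | 1200 | P | 100 |
| 4 | 1200 | 400 | 100 | P |

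Under protocol Section 7.6, "subjects will be randomised to one of four treatment sequences", 1:1:1:1, with a reference back to Section 3.1. Section 7.7 plans 8 subjects per sequence. On the model, Section 7.1 says: "The models will include treatment and period as fixed effects, subject as a random effect"; period and subject baselines are covariates, and there is no carryover term. On washout, Section 3.1 says: "Each period will be separated by a washout period of at least 14 days". Flow chart note 8 adds that in exceptional circumstances "the washout between the two treatment periods can be extended up to a maximum of 8 weeks".

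**The concern.** What separates a Williams square from any other Latin square is that each treatment is immediately preceded by every other treatment equally often. Neither document says this in words, but the name means it, and the table does not deliver it. Section 7.6 sends the randomisation to Section 3.1, which holds both the name and the conflicting table. A list built from the name and a list built from the table would differ, and the randomisation list is not in the documents.

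Two things are at stake:

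- If treatment-dependent carryover occurred, the planned model would not remove it, and the sequences decide which dose contrasts it enters. Section 3.2 gives assessment of a dose-effect relationship as a reason for including three dose levels, so unequal distortion across doses is the relevant risk.
- A reader who trusts the name would expect a carryover-adjusted sensitivity fit to be about equally precise for all three doses. With the printed sequences it is not.

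**Working it through.** **1. The plan's own precision (Section 7.7).** Inputs: N = 32, within-subject SD 0.24 L, two-sided 90% interval, 95% tolerance probability. With df = 3×32 − 6 = 90, the half-width is t(0.95; 90) × SD × √(2/N) × √(χ²(0.95; 90)/90) = 1.662 × 0.24 × 0.25 × 1.121 = 0.0997 × 1.121 = 0.112 L. This reproduces the stated figure. It uses contrast variance 2σ²/32 = 0.0625σ².

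**2. Transition count in Table 3.1:2.** Each treatment stands once in every row and once in every period, so the table is a valid Latin square. There are 4 × 3 = 12 adjacent pairs:

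| Ordered transitions | Times in table | Subjects (8 per sequence) |
|---|---|---|
| P→100, 100→P, 400→1200, 1200→400 | 2 each | 16 each |
| P→1200, 1200→P, 100→400, 400→100 | 1 each | 8 each |
| P→400, 400→P, 100→1200, 1200→100 | 0 | 0 |

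A Williams square has every transition once, hence 8 subjects each. The comparator used below, for arithmetic only, is P-100-1200-400; 100-400-P-1200; 400-1200-100-P; 1200-P-400-100. It contains all 12 transitions once.

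**3. Planned precision.** In both squares treatment is orthogonal to subject and period, so each active-minus-placebo contrast has variance 0.0625σ². Step 1 is unchanged.

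**4. Shift if carryover exists.** Let λ_k be the net carryover from treatment k on the analysed endpoint. The documents give no value, so it is hypothetical. By orthogonality, a contrast shifts by a quarter of the difference in summed carryover received. In the printed table:

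- P follows 100, 100 and 1200.
- 100 follows P, P and 400.
- 400 follows 100, 1200 and 1200.
- 1200 follows 400, 400 and P.

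With λ_P = 0, the shifts as printed are:

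- 100 − P: (λ400 − 2λ100 − λ1200)/4
- 400 − P: (λ1200 − λ100)/4
- 1200 − P: (2λ400 − 2λ100 − λ1200)/4

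In a Williams square the shift is −λ_j/4 for dose j, so each dose's carryover stays in its own contrast.

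| Assumed carryover | Square | 100 − P | 400 − P | 1200 − P |
|---|---|---|---|---|
| Equal λ from all active doses | Printed | −0.50λ | 0 | −0.25λ |
| | Williams | −0.25λ | −0.25λ | −0.25λ |
| Proportional to dose (1/12, 1/3, 1; λ = residual from 1200 µg) | Printed | −0.21λ | +0.23λ | −0.125λ |
| | Williams | −0.02λ | −0.08λ | −0.25λ |
| Common to all four treatments | Both | 0 | 0 | 0 |

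**5. Scale.** Section 7.7 expects a difference of −0.06 L. Under dose-proportional carryover, a shift of that size needs λ = 0.06 divided by the coefficient. As printed this is 0.29, 0.26 and 0.48 L for the three contrasts; in a Williams square it is 2.9, 0.72 and 0.24 L.

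**6. Effect of the baseline covariate.** The dose-proportional case was simulated with 400,000 subjects, fixed subject effects, SD 0.24 L, a 1200 µg residual of 0.1 L and the period baseline as covariate. λ is now the residual at the treatment challenge, and ρ is the assumed within-subject correlation between the two challenges.

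- If the baseline challenge carries no residual, the shifts are as in step 4.
- If the same residual is present at both challenges, they fall by a factor of about 1 − ρ. At ρ = 0.5 they are roughly halved; at ρ = 0.8 none exceeds about 0.05λ in size in either square.
- If the baseline residual is twice the treatment residual, the shifts are about zero at ρ = 0.5 and change sign at ρ = 0.8.

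**7. Carryover-adjusted fit (not planned in either document).** Least squares with a first-order carryover term gives variance 0.206σ² for 100 and 1200 µg and 0.069σ² for 400 µg as printed, against 0.069σ² for all three in a Williams square. At SD 0.24 L and 87 df (t = 1.663), the 90% half-widths are 1.663 × 0.24 × √0.20625 = 0.181 L and 1.663 × 0.24 × √0.06875 = 0.105 L. These carry no tolerance factor; the like-for-like planned value is 0.0997 L, not 0.112 L.

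**The case against.** The strongest reply is that this is a naming slip with little practical weight. The protocol never relies on first-order balance; Section 3.2 explains the term only by noting that the highest dose may come first. Four sequences are printed and Section 7.6 points to four sequences, so the operational instruction can be read as clear, and nothing shows that the randomisation list departs from the table. A Latin square balanced for period is an acceptable choice for an exploratory trial with a washout of at least 14 days and a new baseline challenge in every period. The planned analysis runs identically with either square. Neither square has the smaller bias in every scenario: under dose-proportional carryover the printed one is better for 1200 µg. The sensitivity fit in step 7 is not planned.

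Most of this stands, and it limits the consequence rather than the finding. λ, dose-proportionality and ρ are assumptions. That material carryover is unlikely after 14 days is a judgement, since the public text gives no figure for it. SAP Table 6.2:1 lists improper washout (code C6), but by default this excludes nobody from any analysis set, so it is a weak safeguard.

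The contradiction itself remains. The printed rows are complete and form a valid Latin square, so a broken table is an unlikely explanation. No other passage corrects the name, and the final SAP repeats it.

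**Conclusion.** The concern holds. The name given to the Part 2 design in three places, across both documents, does not fit the only sequences listed: four of the 12 ordered transitions are absent and four occur twice. This follows from the table by counting and needs no assumption. Which of the two is the error cannot be settled without the randomisation list.

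The planned sample size, precision and analysis are unaffected, and no bias in the planned analysis is claimed. Only if treatment-dependent carryover survived the washout would the printed order matter. It would then mix one dose's carryover into other doses' contrasts, by at most half of λ in the scenarios examined, and it would triple the variance of a carryover-adjusted comparison for 100 and 1200 µg (0.206/0.069 ≈ 3) relative to a Williams square. A Williams square would not remove carryover bias; it would only confine each active dose's carryover to its own contrast.

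**What to change.** Reconcile the design name, Table 3.1:2 and the randomisation list before Part 2 subjects are randomised. Either route resolves the contradiction:

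1. If a Williams design was intended, replace the rows of Table 3.1:2 with four sequences in which all 12 ordered transitions occur once, keep 8 subjects per sequence, and check the randomisation list, regenerating it if needed.
2. If the printed sequences were intended, remove the name from protocol Sections 3.1 and 3.2 and SAP Section 6.1, and describe Part 2 as a Latin square balanced for period but not for first-order carryover.

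The cost is a wording change in three places, or one table edit with a check of the list. Subjects, periods, doses and planned precision stay the same.

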3.1.1 Administrative structure of the trial

The trial is sponsored by Boehringer Ingelheim (BI). A Coordinating Investigator has been appointed. The tasks and responsibilities of the coordinating investigator are defined in a contract.

Relevant documentation on the participating Investigators and other important participants, including their curricula vitae, will be filed in ISF.

Boehringer Ingelheim has appointed a Trial Clinical Monitor, responsible for coordinating all required activities, in order to

- manage the trial in accordance with applicable regulations and internal SOPs,
- direct the clinical trial team in the preparation, conduct, and reporting of the trial,
- ensure appropriate training and information of local clinical monitors (CML), Clinical Research Associates (CRAs), and Investigators.

The organisation of the trial will be performed by the respective local BI-organisation (Operating Unit, OPU) in accordance with applicable regulations and internal SOPs.

Data Management and Statistical Evaluation will be done by BI according to BI SOPs.

The review of data generated in Part 1 of the study and confirmation of dose escalation procedures will be performed in accordance with relevant SOPs.

Tasks and functions assigned in order to organise, manage, and evaluate the trial are defined according to BI SOPs. A list of responsible persons and relevant local information can be found in the ISF.

Central and local laboratory services will be used in this trial. Details will be provided in ISF.

3.2 DISCUSSION OF TRIAL DESIGN, INCLUDING THE CHOICE OF CONTROL GROUP(S)

For MCh challenge studies, the crossover design described in [Section 3.1](#) is commonly employed to increase sensitivity due to the within subject comparison. An active comparator is not appropriate for this assessment and a placebo comparison is required as a negative control to quantify the nature of any response observed.

Subjects will be allowed to continue inhaled low dose corticosteroid and SABA use provided washout is undertaken prior to MCh challenge. The subjects will be on standard of care treatment for the severity of their disease and thus the use of placebo in this setting is considered acceptable.

The study will be conducted in two parts: Part 1 in 4 subjects in a dose escalating design and Part 2 in which doses may be administered according to a William's crossover design (i.e. highest may be administered first). Three multiple dose levels of BI 443651 are included, to assess for a dose-effect relationship as observed in the nonclinical studies and also, in part one of the study to allow for effects to be assessed at lower doses prior to subjects being exposed to the highest dose as the initial dose (as may be allowed in Part 2 of the study). For the pilot part (Part 1), it is planned to include 4 asthma subjects. The planned sample size is not based on a power calculation. This sample size is considered sufficient for the initial evaluation of safety post MCh challenge prior to allowing patients to be administered the highest dose of BI 443651 as the first dose level.

For the main part (Part 2), it is planned to include a total of 32 (8 per sequence) subjects with mild asthma, because this sample size is considered sufficient to achieve the aims of this exploratory trial. For more details refer to [Section 7.7](#).

The cumulative bolus dose approach to MCh challenge is used during the treatment phases as the primary outcome is based on drop in FEV1 for a given dose rather than dose of MCh required to achieve a fall in FEV1.

